This is a study where patients will be randomized to two groups. One group will receive Local anesthetic and Tenex. The second group will receive local anesthetic only. The second group will be given the option of crossing over to local anesthetic and Tenex group at 1-month visit. Please note Local anesthetic is standard of care for diagnostic purposes. Both groups will be receiving the same anesthetic.

Subjects shoulder ROM, QOL, VAS and opioid usage will be assessed before and after the procedure in both the groups. These parameters will also be evaluated at the 1-month visits.

Other relevant data will be collected through chart review. This includes patient medical, surgical history, medication history, other health conditions, demographics and exercise/physiotherapy sessions.

Primary outcomes: Improvement in shoulder range of motion (ROM) (external rotation) immediately post procedure by at least 100%

Secondary outcomes:

Sustained ROM at 1-month visit compared to pre-procedure ROM

Opioid use before after and at 1-month visit

VAS scale for an expected difference of 3 points

Quality of life questionnaire before procedure, after procedure and at 1-month visit.

Bilateral shoulder ROM improvements in subjects with bilateral procedure

Target Population: 57 adult patients will be enrolled in the Montefiore Hutchinson campus.

Power Analysis:

Assume 30% of patients in the local anesthetic group will have at least a 100% improvement in range of motion one-month post treatment. With a sample size of 32 patients in the Tenex group and 16 patients in the local

anesthetic group, the study will have 81.9% power to detect a difference of 45% in patients with at least a 100% improvement in range of motion between the Tenex group and local anesthetic group one-month post treatment using a two-sided Fisher's exact test at a 0.05 significance level.

Assume an attrition rate of 15%, 57 patients will be enrolled and randomized in a 2:1 ratio to receive either Tenex or local anesthetics.

Randomization

Block randomization was done using SPSS software by the in house statistician. Randomization is noted at the end of the document for all our patients. Please note randomization is 2:1 Tenex:LA. LA will cross over to Tenex at 1 month if the subjects desire.

Inclusion:

1. Adults >18 and <89 years
2. Established Diagnosis of Adhesive capsulitis (AC)
 - Ligament Flavum >3mm, diagnosed by US evaluation

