 - decreased shoulder ROM in external rotation and abduction (50% of unaffected side) (17)
3. Patients who have tried other conventional therapies like steroid treatments, surgical treatments, physiotherapy with little (defined by less than 20 degrees improvement in shoulder ROM – external rotation) to no improvement in the shoulder ROM

Exclusion:

1. Patients with AC but showing improvement in shoulder ROM progressively (defined by improvement in ROM > 200 external rotation or 20 degrees per week when undergoing physiotherapy)
2. Patients who are currently pregnant
3. less than 18 years old and older than 89 years old

Patient recruitment:

Patients will be identified by the PI/Co-PI and will be consented, screened and enrolled into the study by the approved research staff at the Montefiore Hutchison campus.

Informed consent:

All the subjects will be consented before enrolling into the study. A detailed informed consent is taken by the approved research staff who will explain the study in detail with regards to risks and benefits. The patient can refuse to be a part of the study at any point even after signing the consent.

Benefits:

The patients who are being recruited for this study have limited treatment options and have been suffering from frozen shoulder for years

Possible benefits include

1. Improvement in shoulder ROM
2. Improvement in VAS
3. Improvement in QOL
4. Reduced pain medication usage

Risks:

The procedure is relatively safe as the area near the CHL is relatively avascular. However, there is a risk a rupture of axillary artery. Care will be taken to ensure this does not happen by clear identification of the axillary artery by using USG.

There is a potential this procedure may not improve ROM in which case the study will be stopped, and the IRB will be informed immediately as an adverse event.

Potential for infection, although a minimally invasive procedure there will be a small incision on the skin with potential for infection. All care will be taken to perform the procedure in standard universal precautions. Post procedure the incision will be cleaned, and dressing applied. Standard wound care precautions will be given to the patients.

Study reimbursement: None

Statistical analysis:

Differences in VAS, opioid use, and QOL scores before and after the procedure will be compared using paired t-tests or Wilcoxon singed-rank tests.

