Assume 30% of patients in the local anesthetic group will have at least a 100% improvement in range of motion one-month post treatment. With a sample size of 32 patients in the Tenex group and 16 patients in the local anesthetic group, the study will have 81.9% power to detect a difference of 45% in patients with at least a 100% improvement in range of motion between the Tenex group and local anesthetic group one-month post treatment using a two-sided Fisher's exact test at a 0.05 significance level.

Assume an attrition rate of 15%, 57 patients will be enrolled and randomized in a 2:1 ratio to receive either Tenex or local anesthetics.

Data analysis:

Simple descriptive statistics will be used in analysis of the data. The main primary outcome is the improvement in shoulder ROM and we expect to improve the ROM by at least 100 percent in external rotation. Differences in VAS, pain medication use, and QOL scores before and after the procedure will be compared using paired t-tests or Wilcoxon singed-rank tests.

Data Safety

The PI will give assurances of data safety as well as the timely report of any breach. The data will be stored on a password protected encrypted computer which is located in a locked room with access only to the PI and the research staff. The data reported will be deidentified and any chances of identifying information will be minimized. In addition, the data will be stored on an password protected excel file on the above password protected computers. The identifiers will be destroyed at the end of the study i.e., 3 years from the start of the study.

Subject Safety

In addition to following the inclusion/exclusion criteria, [REDACTED] will be available on the day of the procedure. He will not be scrubbed in to any other case and will be available for immediate back up in case of a medical or surgical complication on the day of the Tenex procedure. Please note he will also be in the same building.

DSMB and DSMP

Data safety monitoring board will be managed by [name], [name] and [name] [name]. All the three above Physicians are independent researchers and practicing clinicians with expertise in managing chronic pain at Montefiore. They are not associated with the study. [name] and [name] practice in Orthopedics and [name] practices Anesthesiology and pain medicine.

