Any adverse events will be immediately reported to them in addition to IRB. They will regularly conduct data monitoring and safety visit every 6 months. In addition, they will assure the safety of research participants and continued relevance of the study question.

DSMP SCHEDULE

1. Adverse events reportable in 48 hours.

2. Safety monitoring every 6 months.
3. Independently report any safety concerns to IRB immediately at any point of the study.
4. They can stop the study if >40% of the study subjects have no improvement in ROM or worsening of ROM at 1-month visit
5. Study withdrawal criteria - worsening of the ROM>40 degrees from baseline in external rotation

References:

1. Wu, C.-H., Chen, W.-S., & Wang, T.-G. (2016). Elasticity of the Coracohumeral Ligament in Patients with Adhesive Capsulitis of the Shoulder. *Radiology*, 278(2), 458–464. doi: 10.1148/radiol.2015150888
4. Le, H. V., Lee, S. J., Nazarian, A., & Rodriguez, E. K. (2017). Adhesive capsulitis of the shoulder: review of pathophysiology and current clinical treatments. *Shoulder & elbow*, 9(2), 75–84. doi:10.1177/1758573216676786

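### The only numeric study-level stopping guide (DSMP item 4) pools both arms, so control patients who have not yet had Tenex dilute and shift it

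*Combined protocol and SAP*

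**What the plan says.** Item 4 of the DSMP SCHEDULE reads "They can stop the study if >40% of the study subjects have no improvement in ROM or worsening of ROM at 1-month visit". It does not define the subjects by arm. The Study Design section uses the same word for everyone: "Subjects shoulder ROM, QOL, VAS and opioid usage will be assessed before and after the procedure in both the groups". On timing it says "The second group will be given the option of crossing over to local anesthetic and Tenex group at 1-month visit", so an LA patient's 1-month reading reflects local anesthetic only.

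The Risks section gives the purpose of stopping: "There is a potential this procedure may not improve ROM in which case the study will be stopped". It attaches no number. Item 5 of the DSMP SCHEDULE has a number (worsening of more than 40 degrees), but it is a withdrawal criterion for a patient. Item 4 is therefore the only numeric guide at study level. On frequency, the DSMB section says "They will regularly conduct data monitoring and safety visit every 6 months".

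**The concern.** The guide is meant to tell the board whether the procedure is failing, yet a third of its denominator has not had the procedure when it is read. LA patients who do not improve count toward stopping. LA patients who do improve offset Tenex patients who fail. The same Tenex result can therefore reach the limit or miss it because of the control arm.

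This could mislead in either direction. If LA failure is common, the number points toward stopping even when Tenex is doing acceptably, and a control arm that fails while Tenex works is the result the trial hopes to show. Common LA failure is plausible because inclusion criterion 3 selects "Patients who have tried other conventional therapies like steroid treatments, surgical treatments, physiotherapy with little" or no gain in ROM, although the plan gives no rate. If LA failure is rare, the number is slow to register Tenex failure. Since the error runs both ways, moving the 40% limit would not cure it.

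**Working it through.** **Inputs from the document**
- Randomization schedule: 19 blocks of three, each with two Tenex and one LA, giving 38 Tenex and 19 LA.
- Power Analysis: 32 Tenex and 16 LA evaluable. It also says "Assume 30% of patients in the local anesthetic group will have at least a 100% improvement in range of motion one-month post treatment" and assumes a 45-point difference, which implies 30% + 45% = 75% doubling on Tenex.
- Item 4: strictly more than 40%.

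**Not in the document:** the rate of no improvement in either arm, and the number of patients at each review. Both are assumed below.

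**The plan's own figures.** Exact enumeration of the two-sided Fisher test (32 v 16, 75% v 30%) gives 81.95% power against the stated 81.9%. Attrition: 48/0.85 = 56.5, rounded up to 57. Both reproduce.

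**Step 1: limits.** The limit is the smallest whole number above 40% of n.
- Pooled, 57: 0.40 × 57 = 22.8, so 23.
- Tenex only, 38: 0.40 × 38 = 15.2, so 16.
- Pooled, 48: 19.2, so 20. Tenex only, 32: 12.8, so 13.

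**Step 2: Tenex failures needed under the pooled rule** = 23 − LA failures. This step needs no assumed rate.

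| LA failures (of 19) | Tenex failures needed (of 38) |
|---|---|
| 0 | 23 (61%) |
| 5 | 18 (47%) |
| 7 | 16 (42%) |
| 10 | 13 (34%) |
| 13 | 10 (26%) |
| 19 | 4 (11%) |

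A Tenex-only count needs 16 in every row. The two rules coincide only when 7 of 19 LA patients fail. At an assumed early review of 8 Tenex and 4 LA, the pooled limit is 5 of 12 (0.40 × 12 = 4.8). That takes 4 of 8 Tenex failures if one LA patient fails, and 2 of 8 if three do.

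**Step 3: illustrative chance of crossing.** With T ~ Bin(32, pT) and L ~ Bin(16, pL), one look gives P(T + L ≥ 20) pooled and P(T ≥ 13) Tenex-only. Four looks are assumed at 8+4, 16+8, 24+12 and 32+16 patients, with pooled limits 5/10/15/20 and Tenex-only limits 4/7/10/13, by exact recursion.

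| Tenex failure | LA failure | One look, pooled v Tenex-only | Four looks, pooled v Tenex-only |
|---|---|---|---|
| 10% | 50% | 0.1% v <0.1% | 10% v 0.5% |
| 10% | 70% | 2% v <0.1% | 25% v 0.5% |
| 25% | 10% | 0.04% v 3.8% | 7% v 17% |
| 25% | 35% | 3% v 4% | 27% v 17% |
| 25% | 50% | 13% v 4% | 46% v 17% |
| 25% | 70% | 46% v 4% | 74% v 17% |
| 50% | 20% | 46% v 89% | 74% v 94% |
| 50% | 50% | 90% v 89% | 96% v 94% |

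Under the design's own assumptions, Tenex 25% (100 − 75) and LA 70% (100 − 30) are both upper bounds, because failing to double ROM is a broader category than failing to improve. Six-monthly reviews over the three years given under Data Safety allow at most 36/6 = 6 looks; four is a choice made here.

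**The case against.** The strongest reply is that little follows from the pooling. Item 4 says the board can stop, not that it must. The Risks section separately provides for stopping if the procedure does not improve ROM, item 3 lets the board go to the IRB at any time, and nothing bars it from looking by arm. Two thirds of the count are Tenex patients. All of that stands. A reader might infer that the guide says nothing about the procedure, or that the board would be forced to stop a working trial or left unable to stop a failing one. The documents support neither reading.

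The crossing probabilities are also open to challenge. The 25%/70% row puts both arms at their ceilings. In that row the assumed first look at 12 patients supplies 57 of the 74 percentage points, and the plan gives no accrual rate. At 25%/35% and one look the rules barely differ. The 50%/20% row needs Tenex patients to do much worse than LA patients although both receive the same anesthetic, which sits badly with a refractory population. These criticisms are fair, so the probabilities serve only as illustration. They do not touch Step 2, which rests on the schedule and the 40% limit alone.

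A last argument is that pooling errs toward caution when LA failure is high. That is true once more than 7 of 19 LA patients fail, but the signal then comes from patients who have not had the procedure being judged.

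**Conclusion.** The concern holds in a limited form. Item 4 pools the arms, and at full enrolment the Tenex failure proportion needed to reach its limit moves between 11% and 61% according to the LA arm alone, against a fixed 42% (16 of 38) for a Tenex-only count. The range needs only the 2:1 schedule, the literal wording of item 4 and the crossover timing. How often this would change what the board sees cannot be settled from the plan, since failure rates and review sizes are not given. It is a misdirected guide within a discretionary process, worth correcting because the correction is small.

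**What to change.** In item 4, replace the reference to study subjects with: *patients randomized to Tenex who have a 1-month reading*. Keep the more-than-40% limit and the board's discretion. Add that an LA patient's 1-month reading before crossover is not counted, and that any ROM reading taken after crossover Tenex is shown to the board separately; the plan states no 1-month visit after crossover, so those readings cannot simply be added to the count. Show the board 1-month ROM by arm at each six-monthly review.

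This needs no new visit or measurement. The price is a smaller count, which crosses more often by chance when LA failure is low: see the 25%/10% row, where crossing rises from 0.04% to 3.8% at one look and from 7% to 17% over four assumed looks. When LA failure is 50% or more, little sensitivity is lost: at Tenex failure 50% over four looks, 94% against 96% (LA 50%) or 99.6% (LA 70%).

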30	3677	10 B
31	2123	11 A
32	4903	11 A
33	9499	11 B
34	1095	12 B
35	1333	12 A
36	8586	12 A
37	1143	13 B
38	5573	13 A
39	8400	13 A
40	4149	14 B
41	8490	14 A
42	8980	14 A
43	187	15 A
44	5888	15 A
45	5961	15 B
46	700	16 A
47	3577	16 A
48	4446	16 B
49	1727	17 A
50	2434	17 A
51	9304	17 B
52	2244	18 B
53	2758	18 A
54	4147	18 A
55	2169	19 A

Obs ID Block Treatment**56** 3367 19 A**57** 4305 19 B**A: Tenex****B: local anesthetic**
